### **Study Treatment Pre-Restart and Restart Visits**

Subjects should be encouraged to restart study treatment whenever possible and appropriate. If the subject has interrupted study treatment for  $\geq 28$  days, Restart Visits are required. The Pre-Restart Visit will be conducted on the day study treatment is resumed, followed by Restart Visits at Weeks 1, 3 (phone visits); 5, and 13 to be scheduled based on the date of study treatment restart. The following procedures will be performed at the Pre-Restart Visit:

1. Directed history (including review of AEs/SAEs, concomitant medications, oxygen use, and hospitalizations, clinical and exposure history).
2. Physical examination, vital signs, and weight.
3. Clinical laboratory assessments, including hematology, serum chemistries, and pregnancy test for women of childbearing capacity.
4. Instruction on how to re-titrate the dose of study treatment.
5. Dispensing of study treatment, as necessary.
6. Dispensing of patient diary, as necessary.

Visit requirements and visit windows for Restart Week 1 and 3 (phone visits) and Restart Weeks 5, and 13 are the same as those described above.

Subjects who restart study treatment will resume the visit schedule based on their date of randomization. If a regularly scheduled visit (Weeks 13, 26, 39, etc.) coincides with one of the Restart Visits (Restart Weeks 5), then all of the elements of the regularly scheduled visit should be performed in lieu of the Restart Visit (see clinical IB section 3).

### **QTc Monitoring**

During the study, if the QTc interval is  $>550$  msec., confirmed by a repeat ECG within 24 h, the study drug will be interrupted until the reading is confirmed by the ECG safety officer. If the reading is confirmed, the subject will be discontinued from study treatment. If the QTc interval is between 500 and 550 msec., confirmed by a repeat ECG within 24 hours, study treatment will be interrupted. If an alternative explanation is identified (e.g., electrolyte abnormality or concomitant medication), re-initiation of study treatment will be considered

by the investigator. ECG data will be entered directly into the research's database.

### **Patients Lost to Follow-Up**

If a subject has missed a visit and is not responding to no more than 2 attempted telephone calls from the site (all attempts to contact the subject should be documented). The site should then make no more than 2 attempts to contact the subject's emergency contact. If these attempts are not successful, a registered letter should be sent to the last known address of the subject. If this is not successful, as a last resort, the site should check the national death registries, where approved by regulatory authorities and available. If this is unsuccessful, the subject will be considered lost to follow-up.

## **STATISTICAL METHODS**

### **Randomization and Treatment Assignment**

In this double-blind study, subjects will be randomized to receive either pirfenidone 2403 mg/d or placebo in a 2:1 ratio.

### **Sample Size and Power Considerations**

The sample size and power calculations for this study are based on the primary endpoint, mean change in %FVC from Baseline to Week 52. Estimates are based on the results from the National Jewish Health pilot data of FHP (N=30 patients with biopsy and HRCT FHP pattern). For the primary efficacy comparison of change in mean %FVC between the treatment (2403 mg/d) and placebo groups, about 13 patients in the placebo and 25 (N=38) in the treatment group will provide at least 85% power to detect a mean difference between groups of 2%. Assuming a 10% attrition rate approximately 42 subjects will be enrolled and randomized in a 2:1 ratio to pirfenidone 2403 mg/d or placebo.

These calculations assume a standard deviation in the %FVC change from baseline to 52 weeks of 2% and are based on a 2-sample means t-test with a 2-sided Type I error probability of 0.05.

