### Study design

This is a single-center, randomized, double-blind, placebo-controlled, efficacy and safety study of pirfenidone in subjects with FHP. Approximately 42 subjects will be randomized in a 2:1 ratio to receive pirfenidone 2403 mg/d or placebo for 52 weeks. The primary efficacy endpoint is the mean change in %FVC from Baseline to Week 52, to be analyzed using a rank linear model. Subjects will receive blinded study treatment from the time of randomization until the Week 52 Visit.

Eligible subjects, males and females, aged 18–80 years (inclusive) must have a confident or high-confidence diagnosis of FHP according to pre-specified criteria without evidence of an alternative diagnosis that may contribute to their interstitial lung disease. Subjects will be required to have a FVC  $\geq$ 40% and DLCO  $\geq$ 30% at screening.

Subjects will enter the Screening Period, which may last up to 30 days. In addition of brief periods of corticosteroid use for acute FHP exacerbation, subjects will be allowed to receive any other therapy for the treatment of FHP as per pre-specified criteria.

The dose of study treatment will be titrated over 4 weeks (2 weeks at 1 capsule TID; 2 weeks at 2 capsules TID; and 48 weeks at 3 capsules TID (2403 mg/d). Pirfenidone dose modifications or interruption will be allowed for safety or tolerability reasons at any time during the study.

Subjects will have a telephone assessment at Week 1 and 3, and an in-clinic assessment at day 1, weeks 5, 13, 26, 39, and 52. Subjects will be asked to complete an adverse event (AE) and dosing compliance diary between all visits. If subjects discontinue study treatment early for any reason, they will be asked to continue with all scheduled study procedures through Week 52.

A Safety officer will review all deaths and monitor subject safety during the study.

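### The stated power of at least 85% with 25 and 13 patients does not follow from the plan's printed inputs; the stated t-test gives 81.2%

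*Combined protocol and SAP*

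**What the plan says.** All the inputs stand in one section of the combined protocol and SAP, Sample Size and Power Considerations.

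- **Endpoint:** "The sample size and power calculations for this study are based on the primary endpoint, mean change in %FVC from Baseline to Week 52".
- **Arm sizes and power:** "about 13 patients in the placebo and 25 (N=38) in the treatment group will provide at least 85% power to detect a mean difference".
- **Effect:** the plan wants "to detect a mean difference between groups of 2" percentage points.
- **Variability:** "These calculations assume a standard deviation in the %FVC change from baseline to 52 weeks of 2" percentage points.
- **Test and alpha:** the calculations "are based on a 2-sample means t-test with a 2-sided Type I error probability of 0.05".

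The section then allows for 10% attrition and arrives at about 42 randomised. The 38 patients are therefore the evaluable number, and the 85% is attached to them. Study design repeats the total: "Approximately 42 subjects will be randomized in a 2:1 ratio". The section on Randomization and Treatment Assignment confirms the unequal allocation. The pilot data on 30 patients, from which the estimates are said to come, are not shown.

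**The concern.** A two-sample t-test has a definite power once the difference, standard deviation, alpha, sidedness and two arm sizes are given, and the plan gives all of them. A reader with standard software who enters these values does not get 85% or more.

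This is the only power figure in the document, and it is the quantitative reason for randomising about 42 patients. The plan commits the trial to CONSORT reporting, so the sample-size rationale can be expected to reappear in the report. If the primary comparison is not significant, readers would judge that result against a sensitivity the design did not have under its own assumptions. The type I error and the planned analysis are not affected.

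**Working it through.** **Inputs** (all from Sample Size and Power Considerations): difference δ = 2 points; standard deviation σ = 2 points; n₁ = 25 on pirfenidone; n₂ = 13 on placebo; two-sided α = 0.05; two-sample t-test. The printed values are taken as exact.

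**Step 1: the plan's own figure, with its own test.**

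- Degrees of freedom: 25 + 13 − 2 = 36. Critical value: t(0.975; 36) = 2.028.
- Noncentrality: λ = δ / [σ√(1/n₁ + 1/n₂)] = (2/2) × √(25 × 13 / 38) = √8.553 = 2.924.
- Power: P(|T| > 2.028), where T is noncentral t with 36 degrees of freedom and λ = 2.924, is **0.812**.

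The stated figure of at least 0.85 is not reproduced. The shortfall is 85.0 − 81.2 = 3.8 percentage points. The type II error is 1 − 0.812 = 18.8%.

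**Step 2: other readings.** All use δ = 2, σ = 2 and α = 0.05.

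| Reading | Arms | Power | Agrees with the plan? |
|---|---|---|---|
| Two-sided t-test | 25/13 | 81.2% | Yes, as stated |
| Two-sided t-test, exact 2:1 | 26/13 | 81.8% | One patient more |
| Two-sided t-test, all randomised, no attrition | 28/14 | 84.6% | Ignores the attrition |
| Welch t-test (simulated, 200,000 runs) | 25/13 | about 80.0% | A variant of the test |
| Normal approximation, two-sided | 25/13 | 83.3% | Not the stated test |
| Normal approximation, two-sided | 27/14 | 85.9% | Neither test nor n |
| Normal approximation, two-sided | 28/14 | 86.3% | Neither test nor n |
| Two-sided t-test, equal arms | 19/19 | 85.1% | Not 2:1 |
| One-sided t-test | 25/13 | 89.0% | Not two-sided |

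No reading that keeps both the stated test and the stated arm sizes reaches 85%. Those that do reach it change the sidedness, the allocation, or both the test and the number of patients.

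**Step 3: what would make 85% true with 25 and 13.** Solving the power equation of Step 1 for 0.85 gives:

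- δ = 2.106 with σ = 2 (δ = 2.10 gives 84.8%, δ = 2.11 gives 85.1%); or
- σ = 1.899 with δ = 2 (σ = 1.90 gives 84.98%).

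**Step 4: what sample size would give 85% with δ = 2 and σ = 2.**

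- At about 2:1: 29/14, 43 evaluable, power 85.1%. At 10% attrition: 43 / 0.9 = 47.8, so 48 randomised.
- At exactly 2:1: 42 evaluable (28/14) falls just short at 84.6%; the next step is 45 evaluable (30/15), power 87.1%, or 45 / 0.9 = 50 randomised.

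Step 4 shows the size of the gap in patients. It is not a proposal to enlarge the trial.

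**The case against.** The strongest objection is rounding. The difference and the standard deviation are printed to one significant figure and come from pilot data that the documents do not show. A standard deviation of 1.90 would be printed as 2 and gives 85.0%; 1.85 gives 86.8%. A difference of 2.2 would also be printed as 2 and gives 87.9%. The authors may have calculated correctly and reported coarsely. This stands as a possible cause, but it does not rescue the sentence: the reader has only the printed values, and rounding can go the other way (a standard deviation of 2.05 gives 79.3%). If it is the cause, the remedy is to print the values used.

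Equal allocation is another possible cause, since 19/19 has the same total of 38 and gives 85.1%. The total may have been found for 1:1 and then split about 2:1. The documents support neither explanation over the other, and the conclusion needs neither.

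It can also be said that the gap is small. Power remains above 80%. If the standard deviation of 2 was estimated from all 30 pilot patients with normal data (an assumption), its 95% interval is about 1.59 to 2.69, and power with 25/13 would run from about 95% down to 56%. That uncertainty is far larger than 3.8 points. This is fair, and it limits the importance of the point, but an uncertain input does not excuse a figure that fails to follow from it.

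Finally, the primary analysis is an adjusted rank regression with deaths ranked worst and multiple imputation, so a t-test figure does not describe it. That is true, but the plan ties its power claim expressly to the t-test, and the claim should be right for that test. The power of the rank model cannot be computed here, because the documents give neither the association between baseline and change nor the error distribution.

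**Conclusion.** The concern holds. With the printed values taken as exact, the stated test with 25 and 13 evaluable patients has 81.2% power, 3.8 points below the stated minimum. By the normal approximation the gap is 1.7 points (83.3%), and the claim still fails. Nothing elsewhere in the document corrects or qualifies the 85%.

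The result assumes normally distributed changes with a common standard deviation, as the plan's own t-test calculation does. It says nothing about the power of the planned rank regression, and it does not make the trial seriously underpowered by its own assumptions. It is a definite error of modest size in a headline design figure, and it should be corrected.

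**What to change.** Change one sentence in Sample Size and Power Considerations, in one of two ways:

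1. Replace the claim of at least 85% with about 81% power (two-sample t-test, 25 versus 13 evaluable patients, difference 2 points, standard deviation 2 points, two-sided 0.05).
2. Keep 85% and print the inputs that support it: a difference of about 2.11 points with a standard deviation of 2, or a difference of 2 with a standard deviation just under 1.90. This is open only if the pilot data support the value.

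In either case, name the allocation and the software or formula used, so that the figure can be reproduced.

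The cost is the one sentence and, under the first option, a slightly less favourable stated power. The sample size, allocation, alpha and analysis do not change.

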## BACKGROUND INFORMATION

Hypersensitivity pneumonitis (HP) is an immunologically mediated form of interstitial lung disease (ILD), in response to inhalation exposure to a large variety of antigens, of varying intensity, clinical presentation and natural history.

In the USA, the one-year prevalence rates for HP range from 1.39 to 2.06 cases per 100,000 persons and incidence rates range from 0.82 to 1.74 cases per 100,000. The prevalence and incidence of HP increased with age. Among adults aged 65 and over, prevalence rates range from 3.63-6.57 cases per 100,000 persons and incidence rates range from 2.41-5.18 cases per 100,000.

A subgroup of patients with HP develops fibrotic HP (FHP), characterized clinically by ventilatory restriction and the presence of chest imaging or pathologic evidence of lung fibrosis. FHP is an irreversible and often progressive disease that distorts the lung architecture and ultimately results in hypoxemia and respiratory failure. The presence of lung fibrosis on HRCT scans and/or in surgical lung biopsy specimens is the strongest predictor of death. When fibrosis is present, the median survival time may be similar to those with IPF (4.9 years; 95% CI, 2.9-7.5). Indeed, FHP shares similarities with the most devastating of the ILD, namely IPF. FHP can lead to end-stage pulmonary fibrosis with excessive collagen and extracellular matrix deposition. Also, IPF and FHP are known to have overlapping clinical manifestations, contributing risk factors (e.g., cigarette smoking, aging) and comorbidities (e.g., pulmonary hypertension), histopathologic features and prognosis. Patients with FHP most commonly present with the insidious onset of progressive exertional dyspnea and a non-productive chronic cough. While patients may encounter periods of clinical, radiologic and functional stability, or slow and gradual progression over many years, others may experience an accelerated decline over months. At any time during the disease course patients may experience acute respiratory exacerbations. These events are unpredictable and sometimes fatal.

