## **Efficacy Analyses**

### **Primary Efficacy Outcome Variable and Analysis**

The primary efficacy analysis will estimate the mean rank change in %FVC from Baseline to Week 52. Data will be analyzed using a rank linear regression model with the rank change in %FVC from Baseline to Week 52 as the outcome variable and rank Baseline %FVC and HP therapy (placebo or pirfenidone) and concomitant immunosuppressive therapy as covariates. The treatment effect will be tested using the Wald test.

The primary efficacy analysis will be tested at an alpha level of 0.05. Missing data due to reasons other than death will be replaced with imputed values using the MICE method (multiple imputation via chained equations). Missing data due to lung transplant will be imputed using the MICE method even if the subject dies after lung transplant.

Subjects with missing assessments due to death will be ranked worse than those who remain alive. Subjects who die will be ranked according to the time until death, with the shortest time until death as the worst rank.

Supportive analyses of the primary efficacy outcome will include the following:

1. Landmark analyses of mean change in %FVC from Baseline to Weeks 13, 26, 39 and 52.
2. Mean rank change in %FVC compared to Baseline across all study time points using a rank linear mixed effects model for repeated measures.

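### The stated power of at least 85% is for a t-test that makes no allowance for deaths; the planned rank analysis, with deaths ranked worst, has about 79-82% with no deaths and less if deaths are similar in both arms

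*Combined protocol and SAP*

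**What the plan says.** Under Sample Size and Power Considerations, the calculation is "based on the primary endpoint, mean change in %FVC from Baseline to Week 52". The calculations "assume a standard deviation in the %FVC change from baseline to 52 weeks of 2" (percentage points) and "are based on a 2-sample means t-test with a 2-sided Type I error probability of 0.05". The evaluable numbers are "about 13 patients in the placebo and 25 (N=38) in the treatment group", and the section claims that these "will provide at least 85% power to detect a mean difference between groups of 2" (percentage points). The only allowance for losses is a general one: "Assuming a 10% attrition rate approximately 42 subjects will be enrolled and randomized in a 2:1 ratio". No death rate is assumed.

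Under Primary Efficacy Outcome Variable and Analysis, the deciding test is a linear regression of the rank of the %FVC change on treatment, ranked baseline %FVC and concomitant immunosuppressive therapy, with a Wald test of treatment. Deaths stay in the analysis: "Subjects with missing assessments due to death will be ranked worse than those who remain alive", with the earliest death ranked lowest. Data missing for other reasons are multiply imputed.

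The documents give no expected 52-week mortality. The Background says of fibrotic disease that "the median survival time may be similar to those with IPF (4.9 years; 95% CI, 2.9-7.5"). It also gives medians of 4.88 and 8.75 years for patients with an unidentified and an identified inciting antigen.

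**The concern.** The power figure describes one test and the trial will be decided by another. A t-test on change in %FVC has no place for a patient who dies. The rank model places each death at the bottom of the scale. If pirfenidone slows FVC decline but does not change who dies within the year, those bottom ranks fall in both arms without regard to treatment and dilute the rank difference. The attrition allowance does not cover this: attrition removes patients, whereas deaths stay in as worst outcomes.

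What is at stake is how a non-significant result is read. In a 42-patient trial described as having at least 85% power, it would be taken as fair evidence against a 2-point effect. If the planned analysis has materially less power, that reading is too strong.

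**Working it through.** **1. The plan's own figure.** Inputs from the sample size section: difference 2, SD 2 (standardized difference 1), 13 vs 25, two-sided 0.05.

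- Noncentrality = 1/√(1/13 + 1/25) = 2.924, with 36 degrees of freedom. Exact t-test power is 81.2%; the normal approximation is Φ(2.924 − 1.960) = 83.3%. Neither reaches 85%.
- At 14 vs 28, all 42 analysed: 1/√(1/14 + 1/28) = 3.055, giving 84.6% (t) or 86.3% (normal).

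**2. Mortality range.** Assumption: constant hazard, so one-year mortality = 1 − 2^(−1/median).

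- 8.75 years: 7.6%
- 4.9 years: 13.2% (confidence limits 7.5 and 2.9 years: 8.8% and 21.3%)

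In 42 patients, 5% is about 2 deaths and 13.2% about 5 to 6. Rates of 0%, 3%, 5% and 10% are added because trial patients may differ from those cohorts.

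**3. Hand check of the dilution.** With no deaths, a random pirfenidone patient does better than a random placebo patient with probability Φ(1/√2) = 0.760, an excess of 0.260 over one half. With equal mortality p, independent of treatment and of FVC, the excess becomes (1 − p)² × 0.260. At p = 0.132 it is 0.753 × 0.260 = 0.196. The null standard error for 14 vs 28 is √(43/(12 × 14 × 28)) = 0.0956. Approximate power is Φ(0.260/0.0956 − 1.960) = 78% with no deaths, and Φ(0.196/0.0956 − 1.960) = 54% at 13.2%.

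**4. Simulation of the planned model.** Survivors' change is Normal with SD 2 and a difference of 2. Deaths are drawn by arm and take the worst ranks in random order of time. Ranks are regressed on treatment, ranked baseline and a binary immunosuppression covariate, tested two-sided at 0.05. Ranges cover t and normal reference distributions and repeated runs (4,000 to 20,000 trials each).

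| Mortality, same in both arms | Power, 14 vs 28 | Power, 13 vs 25 |
|---|---|---|
| 0% | 79-82% | 77-79% |
| 3% | 75-77% | 71-74% |
| 5% | 71-74% | 67-69% |
| 7.6% | 66-68% | 61-64% |
| 10% | 60-64% | 55-59% |
| 13.2% | 53-58% | 50-52% |

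The last column applies deaths on top of the 10% attrition, so it counts them twice if that 10% already includes them.

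**5. How much is due to ranking deaths.** If deaths were dropped instead, the same model at 14 vs 28 would keep about 80% power at 5% mortality and 77% at 13.2%. Compared with the no-death result, the death rule costs about 9 points at 5% equal mortality and about 26 points at 13.2%. The step from 85% down to 79-82% is a separate matter.

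**6. If mortality is not equal (14 vs 28).**

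| Scenario | Power |
|---|---|
| 5% vs 2.5% | 78-81% |
| 10% vs 5% | 75-78% |
| 13.2% vs 6.6% | 75-77% |
| 13.2% vs 0% | about 90% |
| Death correlated 0.5 with actual decline, placebo mortality 3-13.2% | 76-80% |
| Death correlated 0.3 with actual decline, placebo mortality 3-13.2% | 78% falling to 69-70% |

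**7. Sensitivity.** At 13.2% equal mortality with a normal reference, a baseline-change correlation of 0.3 gives 59% instead of 56%; discarding 10% of non-death data gives 49%. With no deaths, the 0.3 correlation and a normal reference give 84.6%.

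**The case against.** The strongest reply is that the large losses rest on two assumptions the documents do not make.

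First, a reader might infer that the protocol itself quotes a one-year mortality of about 13%. It does not. That figure is a constant-hazard conversion of a cohort median which the Background says only may resemble that of IPF. The identified-antigen median converts to 7.6%. Entry requires FVC of at least 40%, DLCO of at least 30% and a walk of at least 100 m, and excludes patients listed for or expecting transplant, all of which point to lower mortality. The requirement for evidence of progression points the other way. Mortality in this trial is therefore unknown.

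Second, the lowest figures need a drug that gives the full 2-point FVC benefit and has no effect on death. If death follows the decline that the drug slows, the loss from the death rule is about 0-4 points at a correlation of 0.5 and 2-11 points at 0.3.

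Both points stand, and they limit the size of the loss. They do not rescue the stated figure. The sample size section assumes no mortality benefit, so equal mortality is a case it has to cover, and even with no deaths the planned model has about 79-82%. A further objection, that the 10% attrition may already include deaths, cannot be settled from the text; that is why the main results use all 42 patients.

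**Conclusion.** Wrong as written. The claim of at least 85% power belongs to a test that will not decide the trial, and that test does not reach 85% at the stated numbers. For the planned analysis with 42 patients, power at the assumed effect is about 79-82% with no deaths and 53-77% for equal mortality between 13.2% and 3%. It is about 69-81% if mortality is halved or death follows decline. Only a larger mortality benefit clearly restores 85%.

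A reader might go further and conclude that the death rule brings power down to about even odds. The documents do not support that as a general statement: it holds only near 13% mortality with no drug effect on death, and part of the gap from 85% exists before any death is counted. Nor does this show that ranking deaths worst is a poor choice; it is a legitimate way to handle death, and the fault lies in the power statement. The results rest on the plan's difference and SD, Normal changes among survivors, and the assumed mortality scenarios.

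**What to change.** In Sample Size and Power Considerations, replace the t-test power statement with power simulated for the planned primary analysis: rank of change, ranked baseline, immunosuppression covariate, deaths ranked worst. Give it over a stated range of one-year mortality by arm (for example 0-13%), covering both equal mortality and reduced mortality on pirfenidone. Say whether the 10% attrition includes deaths. Keep 42 subjects and the death rule, and state the lower power.

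The cost is a short simulation and a change of wording, with no extra patients. The downside is a less favourable stated power.
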